2.2.2. Secondary endpoints

- Rate of pathologic response.
- Rate of surgical excision with negative margins.
- Response rate (complete, partial, overall) of the combination therapy prior to surgery, as defined by RECIST 1.1 criteria.
- Pattern of and time to local vs. distant recurrences.

- Relapse-free and overall survival at various time points from study entry.
- Safety and tolerability of combined treatment regimen.
- Rate of treatment discontinuation prior to neoadjuvant radiation therapy.

2.2.3. Exploratory endpoints

- Assessment of changes in activation of molecular pathways associated with MET genetic profiles associated with treatment response and with relapse-free survival.
- Assessment of mutational status of signaling pathways, including MAP-Kinas and AKT/m-TOR pathways.
- Assessment of changes in infiltration of immune cell subsets (CD4, CD8, myeloid) in the immune microenvironment induced by this neoadjuvant treatment, in comparison to matched specimens obtained from the University of Washington pathology archives.
- Radiomic studies to identify predictors of treatment response and relapse-free survival, when comparing pre-treatment imaging with imaging prior to surgery (after completion of radiotherapy and concurrent cabozantinib).

3. STUDY DESIGN

This is an open label, dose-finding, single-arm, prospective phase 1/2 study to identify the recommended dose of cabozantinib given orally, once daily, in a 21-day cycle, plus radiation therapy in subjects with high-risk soft tissue sarcoma of the extremities.

The study will be conducted in compliance with International Conference on Harmonization (ICH) Good Clinical Practices (GCPs).

3.1. Dose-finding Phase 1 Portion of the Study:

Dose levels of cabozantinib will be tested in cohorts of 3 subjects each using the 3+3 dose-finding design.

Table 1. Dose Levels of Cabozantinib

Dose Levels	Daily Dose of Cabozantinib
-1	20 mg daily
0	40 mg daily
+1	60 mg daily

In the dose-finding Phase 1 portion of the study, subjects will receive one week of therapy at the planned starting dosage as monotherapy prior to initiation of radiotherapy. Starting at Cycle 1 Day 8, subjects will initiate therapy concurrently with radiation therapy. Subjects enrolled to phase 1 who withdraw prior to initiation of radiation therapy for any reason, or during the DLT period for reasons other than toxicity will be considered non-evaluable and will be replaced. A window of + 7 days is permitted for initiation of RT in relation to C1D8. It is recommended that subjects begin treatment on a Monday due to radiation scheduling, however this is not mandatory. At least 7 days must pass between C1D1 and initiation of radiation therapy.

In the dose-finding Phase 1 portion of the study, dose levels of cabozantinib will be tested in cohorts of 3 subjects each using the 3+3 dose-finding design, with the starting dose of 40mg once daily, with potential dose escalation to 60 mg, or de-escalating to 20 mg daily. The daily dose of cabozantinib will not be increased to more than 60 mg per day. The DLT period will include all subjects enrolled to the phase 1 component of the study. The DLT period is defined as beginning on C1D8 and continuing until 28 days after completion of concurrent radiation therapy and cabozantinib. If no dose-limiting toxicity (DLT) is observed at the starting dose in the first 3 subjects, the next dose cohort would enroll subjects at 60 mg. If 1 DLT is observed any dose cohorts in the first 3 subjects, then additional 3 subjects will be enrolled at that dose level. If ≤ 1 of 6 subjects experience a DLT at the starting dose or higher, enrollment would continue to the next higher dose level. The first 3 subjects of each cohort must complete their DLT period prior to expanding the cohort to include additional subjects to ensure a second DLT is not seen in the first 3 subjects. If ≤ 1 of 6 subjects experience a DLT at the starting dose or higher, enrollment would continue to the next higher dose level.

If ≥ 2 subjects experience a DLT at dose level higher than the starting dose, enrollment will be discontinued for that dose cohort and the previous dose level would be declared the maximum

tolerated dose (MTD). If ≥ 2 subjects experience a DLT at the starting dose of 40 mg once daily (and any lower dose level), further enrollment at that dose level will be discontinued and cabozantinib will be reduced to the next planned dose level.

If a subject is considered Not Evaluable due to withdrawal for reasons other than toxicity during the DLT Period, they will be replaced.

The MTD of cabozantinib is the highest dose level at which ≤ 1 of 6 (or 0 out of 3) subjects experienced a DLT, thus a target DLT rate of roughly 17%. It is possible that the MTD is not reached in this study (e.g., if no DLT observed in the first 3 subjects at 60 mg daily). Recommended Phase 2 dose (RP2D) is identified based of the totality of safety and efficacy data. Once the dose-finding portion of the study is concluded and RP2D is identified, subjects receiving a lower dose may be allowed to receive cabozantinib at the RP2D, based on the investigator judgment.

3.2. Dose Expansion Phase 2 Portion of the Study:

The dose-expansion Phase 2 will be conducted using an open-label, single stage design. Subjects enrolled in the Phase 1 dose-escalation component of the study at the RP2D level and meeting all inclusion/exclusion criteria for the Phase 2 component of the study will be included for efficacy and safety evaluation in the Phase 2 efficacy component of the study.

Subjects enrolled to the dose-expansion Phase 2 portion of the study will receive one week of cabozantinib monotherapy at the RP2D prior to initiating radiation therapy. Starting at Cycle 1 Day 8, subjects will initiate therapy concurrently with radiation therapy. Subjects enrolled to phase 2 who withdraw prior to initiation of radiation therapy will not be considered evaluable and will be replaced. A window of ± 7 days is permitted for initiation of RT in relation to C1D8. It is recommended that subjects begin treatment on a Monday due to radiation scheduling, however this is not mandatory. At least 7 days must pass between C1D1 and initiation of radiation therapy.

3.3. Study Duration, End of Study, End of Treatment, End of Treatment Visit, Follow-up Period

The study is expected to take approximately 60 months from first subject enrolled to last subject follow-up, including approximately 36 months of enrollment period, an estimated 5 months of treatment (or until treatment is no longer tolerated).

End of Treatment (EOT) for a subject is defined as the date of the last dose of cabozantinib. End of Treatment Visit for a subject is when safety assessments and procedures are performed after the date of the last dose of cabozantinib.

30-Day Follow-Up for a subject is defined as 30 days (± 1 week) after the last dose of cabozantinib. This visit will include safety assessments.

Follow-up period is the on-study time period after the EOT Visit.

The End of Study (EOS) defined as either the date of the last visit of the last subject to complete the study, or the date of receipt of the last data point from the last subject that is required for primary, secondary, and/or exploratory analysis, as pre-specified in the protocol, whichever is later.

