SAMPLE SIZE ESTIMATE	
Phase I/Dose Escalation: Expected 6, but up to 12 subjects to identify the MTD. Subjects enrolled to Phase 1 who withdraw for reasons other than toxicity during the dose-limiting toxicity (DLT) period will be determined to be not evaluable and will be replaced.
 
Phase II/Dose Expansion: 34 additional subjects
 
For sample size determination, we assume the following:
 
Null hypothesis: 1-yr RFS=75%
 
Alternative hypothesis: 1-yr RFS=0.90
 
Alpha=0.1 (one-sided)
 
Beta=0.1 (power=90%)
 
Total accrual=40 evaluable subjects.
 
Anticipate accrual of 6 evaluable subjects from phase I component of study.
 
34 subjects to accrue in phase II portion of study.
 
Assuming 10% non-evaluable rate, 44 subjects would be accrued to the efficacy component of the study to yield 40 evaluable subjects. Subjects enrolled to Phase 2 who withdraw for toxicity during the initial lead-in cycle will be determined to be not evaluable and replaced.

DURATION OF TREATMENT AND STUDY PARTICIPATION	The study is expected to take approximately 36 months from first subject enrolled to last subject follow-up, including approximately 12 months of enrollment period, an estimated 5 months of treatment.

TABLE OF CONTENTS

PROTOCOL SYNOPSIS.....	3
LIST OF ABBREVIATIONS AND DEFINITIONS OF TERMS.....	11
1. INTRODUCTION.....	15
1.1. Soft Tissue Sarcoma.....	15
1.1.1. Epidemiology	15
1.1.2. Standard Treatment	15
1.1.3. Use of radiotherapy in adjuvant and neo-adjuvant therapy.....	16
1.1.4. Use of chemotherapy in adjuvant and neo-adjuvant therapy	17
1.1.5. Use of chemoradiotherapy in adjuvant and neo-adjuvant therapy.....	19
1.2. Cabozantinib Background	22
1.3. Rationale for Combination of Cabozantinib with Radiation Therapy for High-Risk Soft Tissue Sarcoma of the Extremities.....	23
1.4. Rationale for Starting Dose Selection.....	24
2. STUDY OBJECTIVES AND ENDPOINTS	25
2.1. Objectives	25
2.1.1. Primary Objectives.....	25
2.1.2. Secondary Objective(s)	25
2.1.3. Exploratory Objective(s)	25
2.2. Endpoints	25
2.2.1. Primary Endpoints	25
2.2.2. Secondary endpoints	25
2.2.3. Exploratory endpoints	26
3. STUDY DESIGN	27
3.1. Dose-finding Phase 1 Portion of the Study:.....	27
3.2. Dose Expansion Phase 2 Portion of the Study:.....	28
3.3. Study Duration, End of Study, End of Treatment, End of Treatment Visit, Follow-up Period.....	28
4. STUDY POPULATION	30
4.1. Number of Subjects	30
4.2. Inclusion Criteria.....	30

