Follow-up Period	Follow-up period is the on-study time period after the EOT Visit. All subjects that discontinue study drug and have not withdrawn full consent to participate in the study will continue in the follow-up phase for disease recurrence. Follow up will continue approximately every 12 weeks (± 2 weeks), until either one (1) year has elapsed since initiation of cabozantinib therapy (C1D1), death, withdrawal of consent, disease recurrence, or the study closes, whichever is the earliest. This will include a physical exam and imaging assessment. Thereafter, subjects who will be followed every 6 months (+/- 1 month) until 3 years have elapsed since initiation of cabozantinib therapy (C1D1), end-of-study, death, or withdrawal of consent, whichever is earliest. This evaluation may be made by review of publicly available information, record review and/or telephone contact.
Primary Analysis	For this study will occur once all data for primary and secondary endpoints is collected.
Efficacy Analysis Dataset	This includes all subjects treated with at least one dose of cabozantinib at the recommended phase 2 dose, concurrently with neoadjuvant radiation therapy.
Full Analysis Set	All enrolled subjects who receive at least 1 dose of cabozantinib (treated population). Subjects enrolled to Phase 1 who withdraw for reasons other than toxicity during the DLT Period will be considered not evaluable and will be replaced.

Per-protocol Analysis Set	All enrolled subjects who do not have any prospectively defined protocol violations. Subjects enrolled to Phase 1 or Phase 2 who are unable to tolerate cabozantinib monotherapy will not be considered evaluable for the Phase 1 or 2 component of the study and will be replaced. Subjects enrolled to Phase 1 who withdraw for reasons other than toxicity during the DLT Period will be considered not evaluable and will be replaced.
Progression-free survival	The time from the first dose date to the first observation of a disease progression or death due to any cause.
Overall survival	The time from the first dose date to the date of death due to any cause.

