Determination and attribution of DLT are critical for determining the RP2D for this study. The DLT period will include all subjects enrolled to the phase 1 component of the study who receive cabozantinib in combination with radiation therapy. The DLT period is defined as beginning on C1D8 and continuing until 28 days after completion of concurrent radiation therapy and cabozantinib. Cabozantinib is anticipated to have systemic effects at sites distant from that receiving neoadjuvant radiation treatment. It may also interact loco-regionally at the site of radiation administration. However, as the objective of this study is to assess the impact of the cabozantinib/radiotherapy combination, only those effects in the region subject to radiation therapy are considered pertinent and will be considered DLT.

DLT are defined as any Grade 3 or greater AE, occurring in the region subject to radiation therapy, at least possibly related (per investigator attribution) to concurrent radiation therapy and cabozantinib therapy. Toxicities with a clearly identified and documented alternative explanation may be deemed non-DLT. Toxicities which are clearly identified and documented as related to cabozantinib therapy only or radiation therapy only may be deemed non-DLT. Only toxicities observed in the region subject to radiation therapy will be considered DLT.

Toxicities that are Grade 3 or greater that meet the following will always be considered DLT:

1. Occur after the initiation of concurrent cabozantinib/radiation therapy until 28 days after completion of radiation therapy;
 - a. Involve the region of a subject's body that is receiving concurrent radiation therapy; and
 - b. Are of a degree or character inconsistent with anticipated radiation effects.

Dose modification guidelines are outlined in Table 5, Table 6, and Table 8 for clinically significant toxicities that are deemed to have a relation to cabozantinib. Clinically significant toxicities that are deemed to have a relationship to radiation therapy only will be managed per standard institutional practice, additional information is available in Section 10.3.

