12.4. Sample Size Considerations

Phase 1: up to 12 subjects to identify the MTD, but the MTD may be reached with as few as 5 subjects.

Phase 2: For sample size determination, we assume the following:

- Null hypothesis: 1-yr relapse-free survival (local and distant) =75%
- Alternative hypothesis: 1-yr relapse-free survival (local and distant) =90%
- Alpha=0.1 (one-sided).
- Beta=0.1 (power=90%)

Total accrual=40 evaluable subjects.

Anticipate accrual of 6 evaluable subjects from phase I component of study. Therefore, 34 evaluable subjects to accrue in phase II portion of study. Subjects who withdraw for reasons other than toxicity during the DLT Period will be determined to be not evaluable and will be replaced.

Subjects are evaluated for efficacy assessment if they receive at least one dose of cabozantinib in combination with neoadjuvant radiation therapy.

Assuming a 10% drop-out/non-evaluable rate, 44 total subjects would be accrued to the efficacy component for the study to yield 40 evaluable subjects.

From the perspective of efficacy, this study is intended as a screening study of activity. Thus, avoiding a type II error (rejecting the proposed regimen as inactive, when it is an active regimen) is a major consideration. This study is not intended to provide definitive evidence of activity. Therefore, a type I error (false positive) is not considered as critical. For these reasons, we have chosen to increase the power of the study to 90% (minimizing type II errors), while relaxing constraints regarding type I. Specifically, we use a one-sided alpha of 0.10 for rejection of the null hypothesis. Use of a one-sided value is justified based on the high efficacy for *local* control of soft tissue sarcoma provided by the combination of surgery and neoadjuvant radiation therapy (~90%). It is not anticipated that distant disease control would be worsened by addition of cabozantinib to neoadjuvant radiation therapy.

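### The Phase 1 replacement rule has no exception for a subject whose DLT has already been observed, so read literally it discards that subject and conflicts with the 3+3 count

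*Combined protocol and SAP*

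**What the plan says.** Section 3.1 has two replacement limbs for Phase 1. The first covers withdrawal before radiation begins, for any reason. The second covers subjects who withdraw later, "or during the DLT period for reasons other than toxicity will be considered non-evaluable and will be replaced". The same section repeats the second limb directly after the escalation rules: "If a subject is considered Not Evaluable due to withdrawal for reasons other than toxicity during the DLT Period, they will be replaced".

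The second limb also appears in:
- the Synopsis, under the sample size estimate: "who withdraw for reasons other than toxicity during the dose-limiting toxicity (DLT) period will be determined to be not evaluable and will be replaced";
- the definitions of the Full Analysis Set and the Per-protocol Analysis Set, and section 4.1: "Subjects enrolled to Phase 1 who withdraw for reasons other than toxicity during the DLT Period will be considered not evaluable and will be replaced";
- section 12.4: "Subjects who withdraw for reasons other than toxicity during the DLT Period will be determined to be not evaluable and will be replaced".

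No version says what happens when a DLT came before the withdrawal.

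The window is given in sections 3.1 and 10.2.1: "The DLT period is defined as beginning on C1D8 and continuing until 28 days after completion of concurrent radiation therapy and cabozantinib". The dose decisions are in section 3.1: "If 1 DLT is observed any dose cohorts in the first 3 subjects, then additional 3 subjects will be enrolled at that dose level"; two or more subjects with a DLT close the dose level; at most 1 of 6, or 0 of 3, lets it pass.

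**The concern.** Replacement is meant for subjects whose DLT status is unknown because they left before the window closed. A subject who has had a DLT has a known status, and nothing later in the window can change it. The rule does not separate the two cases. A subject with a DLT who then leaves for a reason recorded as something other than toxicity falls under the same sentence as a DLT-free subject who moves away. The trial is open-label, and that reason is recorded after the DLT is known.

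The protocol leaves room for this to happen. Section 7.1.2 (Table 6) manages a Grade 3 event by interruption or dose reduction, so a DLT need not end participation, and the window runs for weeks afterwards. Cohorts have three to six subjects, so one subject can decide whether a dose level is expanded or passed, and the dose chosen is then given in Phase 2.

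**Working it through.** **The plan's own Phase 1 figures.** The target rate of roughly 17% is 1/6 = 16.7%. The range of 5 to 12 subjects also reproduces. The minimum is two DLTs in the first two subjects at the starting dose, then three DLT-free subjects one level down (2 + 3 = 5). The maximum is two full cohorts of six (6 + 6 = 12). Neither figure is in dispute.

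**Length of the window.** Radiation starts on D8 to D15 (section 3.1) and takes 25 to 28 weekday fractions (section 7.2.4). With a Monday start and no interruption:
- earliest end: D8 + 32 days = D40; plus 28 days = D68;
- latest end: D15 + 37 days = D52; plus 28 days = D80.

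The window therefore lasts about 60 to 72 days from C1D8. This takes cabozantinib as ending with radiation.

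**Which limb applies.** A DLT must arise in the irradiated region and be at least possibly related to concurrent treatment (section 10.2.1). The pre-radiation limb therefore cannot reach a subject with a DLT; only the second limb can.

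**One cohort.** One of the first three subjects has a DLT, so section 3.1 calls for three more at that level. Suppose that subject then withdraws for another reason and is replaced by a DLT-free subject. If the withdrawn subject is not counted, the cohort reads 0 of 3 and the level passes without expansion. If the subject is counted, the level is expanded.

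**Chance that a dose level passes.** With a DLT rate p among counted subjects, the level passes on 0 of 3, or on 1 of 3 followed by 0 of 3:

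P(pass) = (1 − p)³ + 3p(1 − p)² × (1 − p)³

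At p = 0.33 this is 0.301 + 0.444 × 0.301 = 0.434.

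Let w be the share of DLT subjects dropped and w0 the share of DLT-free subjects replaced. The DLT rate among counted subjects becomes

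p′ = p(1 − w) / [p(1 − w) + (1 − p)(1 − w0)]

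The documents give neither w nor w0 for the DLT window. Both are assumptions.

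| True rate 0.33 | p′ | P(pass) |
|---|---|---|
| All subjects counted, no withdrawals | 0.330 | 0.434 |
| w0 = 10%, w = 10% | 0.297/(0.297 + 0.603) = 0.330 | 0.434 |
| w0 = 10%, w = 20% | 0.264/(0.264 + 0.603) = 0.304 | 0.485 |
| w0 = 10%, all DLTs kept (w = 0) | 0.330/(0.330 + 0.603) = 0.354 | 0.390 |

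The result depends on the assumptions. With no DLT-free withdrawal (w0 = 0), w = 10% gives 0.480 and w = 20% gives 0.530. At the plan's target rate of 1/6, w0 = 10% and w = 20% give p′ = 0.133/(0.133 + 0.750) = 0.151, and the pass probability moves from 0.780 to 0.81.

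**The case against.** The strongest answer is that no sentence removes an observed DLT from the count. Section 3.1 counts subjects who experience a DLT, not evaluable subjects. Its closing trigger of two or more has no denominator, and it says that the DLT period includes all subjects enrolled in Phase 1. On that reading the DLT stays counted and replacement merely adds a subject. A sensible team might apply it so. This stands in part: a reader might infer that the protocol orders the DLT to be deleted, and it does not say so outright. But nothing in section 3.1 overrides the repeated statement that the subject is non-evaluable and replaced, so the count is left unresolved.

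Four further inferences go beyond the documents:
- *That 2 of 3 readily becomes 1 of 3, or 2 of 6 becomes 1 of 6.* Each change needs a DLT-free replacement. It also needs the withdrawal to come before the second DLT closes the dose level, and no text allows a closure to be reversed.
- *That the plan assumes 10% withdrawal in Phase 1.* Its 10% is the non-evaluable rate for the efficacy component (44 subjects to yield 40).
- *That DLT subjects leave for other reasons more often than DLT-free subjects.* Nothing supports this. Many such departures might well be recorded as toxicity. With equal rates the average pass probability does not move.
- *That section 10.2.1 makes every in-field Grade 3 event a DLT without exception.* The sentence "Toxicities that are Grade 3 or greater that meet the following will always be considered DLT" carries a further condition: the effect must be inconsistent with anticipated radiation effects. The general definition in that section has no such condition, and the point rests on that definition.

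There are also safeguards. The recommended dose rests on the totality of the data, the safety set includes all treated subjects (section 12.1), the monitoring committee reviews adverse events (section 16.1), and the dose is capped. These reduce the consequence. They do not settle who is counted.

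**Conclusion.** The point holds as a conflict in the stated rule. After radiation starts, evaluability depends on the reason for withdrawal alone. Read literally, this sets aside a complete DLT observation that the escalation rule counts. The result in a single cohort can change, for example from 1 of 3 to 0 of 3, provided the replacement is DLT-free.

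The size cannot be established from the documents. On the assumption of a true DLT rate of 33% and 10% withdrawal among DLT-free subjects, the pass probability stays at 0.434 if 10% of DLT subjects are dropped and rises to 0.485 if 20% are. A reader might infer that the rule will send a dose already ruled out into Phase 2. The documents do not support that: they neither state that the DLT is deleted nor show that such withdrawals would be common. This is a correction to make because it is cheap and bears on the count that sets the dose.

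**What to change.** In section 3.1 (both sentences), the Synopsis, the two analysis-set definitions, section 4.1 and section 12.4, limit the second limb to subjects who withdraw in the DLT period for reasons other than toxicity *and without having had a DLT*. Then add: *A subject who has had a DLT is evaluable and remains in the 3+3 count whatever the reason or time of later withdrawal.*

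Leave unchanged the separate rules for withdrawal before radiation (section 3.1) and for subjects who cannot tolerate monotherapy (section 4.1). A general statement that only DLT-free withdrawals for other reasons are replaced would contradict both.

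The change is one clause and one sentence. It alters no dose, DLT definition or sample size. The statistical cost is slight conservatism, because DLT subjects who leave are counted while DLT-free subjects who leave are replaced: about 0.39 rather than 0.43 at a true rate of 33% with an assumed 10% DLT-free withdrawal.

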2. STUDY OBJECTIVES AND ENDPOINTS

2.1. Objectives

2.1.1. Primary Objectives

- Phase I: To determine if administration of cabozantinib is safe and feasible in combination with neoadjuvant radiation therapy.
- Phase II: To assess the proportion of subjects alive and free of both local and distant disease recurrence (and progression after incomplete resection) one year after treatment initiation.

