4. STUDY POPULATION

4.1. Number of Subjects

Phase 1: Up to 12 subjects to identify the MTD, but the MTD may be reached with as few as 5 subjects. Subjects enrolled to Phase 1 or Phase 2 who are unable to tolerate cabozantinib monotherapy will not be considered evaluable for the Phase 1 or 2 component of the study and will be replaced. Subjects enrolled to Phase 1 who withdraw for reasons other than toxicity during the DLT Period will be considered not evaluable and will be replaced.

Phase 2: An anticipated 34 subjects will accrue in Phase 2 of study.

Assuming a 10% drop-out/non-evaluable rate, 44 total subjects would be accrued to the efficacy component for the study to yield 40 evaluable subjects. Subjects enrolled to Phase 2 who withdraw prior to initiation of radiation therapy will be determined to be not evaluable and replaced.

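### Phase 1 subjects who stop or are reduced for out-of-field toxicity after radiation starts stay in the 3+3 count as non-DLTs, so under-exposed subjects can mask in-field DLTs

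*Combined protocol and SAP*

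**What the plan says.** **Replacement.** Section 3.1 makes non-evaluable those Phase 1 subjects who "withdraw prior to initiation of radiation therapy for any reason, or during the DLT period for reasons other than toxicity will be considered non-evaluable". It then repeats the rule for the DLT period: "If a subject is considered Not Evaluable due to withdrawal for reasons other than toxicity during the DLT Period, they will be replaced". Section 4.1 adds that subjects "unable to tolerate cabozantinib monotherapy will not be considered evaluable for the Phase 1 or 2 component of the study and will be replaced".

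**DLT.** Section 10.2.1: "DLT are defined as any Grade 3 or greater AE, occurring in the region subject to radiation therapy", at least possibly related to the combination. It also states: "Only toxicities observed in the region subject to radiation therapy will be considered DLT". The same section expects systemic effects away from the field and sets them aside because the aim is to assess the combination.

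**Decisions.** In Section 3.1, escalation and the MTD follow from 0 of 3 or at most 1 of 6 subjects with a DLT. The RP2D is chosen on all safety and efficacy data.

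**Who is in the DLT period.** Section 3.1: "The DLT period will include all subjects enrolled to the phase 1 component of the study". Section 10.2.1 includes only those who receive cabozantinib with radiation.

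**The concern.** A 3+3 count is informative about a combination only if the subjects scored as DLT-free had enough of it for a DLT to appear. Here a toxicity exit after radiation starts is off the replacement list, and if the toxicity lies outside the field it cannot be a DLT. The subject fills a place in the cohort and adds nothing to the DLT count.

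The protocol itself makes such exits plausible. Section 10.2.1 puts steady state at about two weeks after the first dose and lists several early-onset systemic toxicities. Table 6 and Table 8 call for interruption, reduction or discontinuation for many of them.

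At stake is the Phase 1 objective, "To determine if administration of cabozantinib is safe and feasible in combination with neoadjuvant radiation therapy". Early exits can lower the observed in-field DLT count and let a level pass more often than its true in-field rate warrants.

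**Working it through.** **1. How each kind of Phase 1 subject is handled**

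- Withdraws before radiation, any reason: replaced (3.1; 4.1 for intolerance of the lead-in).
- Withdraws in the DLT period, reason not toxicity: replaced (3.1, 4.1, 12.4).
- In-field Grade 3+ event, at least possibly related to the combination: DLT (10.2.1).
- Withdraws after radiation starts for out-of-field toxicity: not on the replacement list, not a DLT. Stays in the denominator as a non-DLT.
- Reduced, or stops cabozantinib but stays on study, for out-of-field toxicity: same result.

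No section sets a minimum exposure for DLT evaluability or makes discontinuation, reduction or missed doses a DLT. The fourth and fifth lines are a joint reading; no single sentence states them.

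**2. The plan's own figures**

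1/6 = 16.7%, which matches the target DLT rate of roughly 17% in 3.1. The most subjects over two levels is 6 + 6 = 12. The fewest that identify an MTD is 3 (no DLT) + 2 (two DLTs) = 5. Both match 4.1.

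**3. Chance that a level passes**

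With p the per-subject rate of counted DLTs:

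P(pass) = (1−p)³ + 3p(1−p)²(1−p)³ = (1−p)³ + 3p(1−p)⁵

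**4. Masking, extreme case**

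Let r be the true in-field DLT rate with adequate exposure and q the share who stop for out-of-field toxicity after radiation starts. Both are assumptions; the documents give neither. If stopping removes all chance of an in-field DLT, and q is independent of r, the counted rate is p = r(1−q).

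| r | q | p | P(pass) as counted | P(pass) at r |
|---|---|---|---|---|
| 30% | 20% | 0.24 | 0.439 + 0.183 = 0.62 | 0.343 + 0.151 = 0.49 |
| 30% | 30% | 0.21 | 0.493 + 0.194 = 0.69 | 0.49 |
| 30% | 40% | 0.18 | 0.551 + 0.200 = 0.75 | 0.49 |
| 10% | 20% | 0.08 | 0.779 + 0.158 = 0.94 | 0.729 + 0.177 = 0.91 |
| 10% | 30% | 0.07 | 0.804 + 0.146 = 0.95 | 0.91 |
| 10% | 40% | 0.06 | 0.831 + 0.132 = 0.96 | 0.91 |

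**5. Other end of the range**

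If stopping leaves in-field risk unchanged, p = r and the count is not biased.

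**6. What replacement does**

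If under-exposed subjects without a DLT are replaced, P(pass) returns to the last column for every q. This removes the masking. It does not make the 3+3 respond to the exits themselves.

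**7. The gap at the start of the window**

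The DLT period opens on C1D8, but radiation may start up to 7 days later. A toxicity withdrawal in that gap is replaced under the first rule in 3.1 (before radiation, any reason). It is not covered by the later sentence in 3.1 (DLT period, reason not toxicity).

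**The case against.** The in-field limit is deliberate and reasoned in 10.2.1, so the count follows the protocol's own definition. This stands, and the fix leaves the definition alone.

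Passing the 3+3 does not fix the Phase 2 dose. Section 3.1 uses all the data for the RP2D, 12.1 monitors dose changes and discontinuations in all treated subjects, and 16.1 provides committee review. This stands for the RP2D, but none of these sections ties such data to escalation or the MTD.

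A subject who stops cabozantinib may continue radiation and remain under observation, and 1.4 cites a half-life of 99 hours, so exposure does not end with the last tablet. A reduced subject still receives the combination. This stands in part: the true bias lies between steps 4 and 5 of the working. But observation can also be cut short. Suppose radiation starts on a Monday, day 8, with 25 weekday fractions. The last fraction falls on day 40, and 28 days after radiation is day 68. If the last cabozantinib dose is on day 15, routine AE collection under 10.1 and 12.1 ends on day 15 + 30 = 45.

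At a 10% in-field rate the effect is about 4 points even in the extreme case, and the stopping rates are assumed. Both are true; the effect is material mainly when the true in-field rate is high.

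The difference between 3.1 and 10.2.1 on who is in the DLT period has limited effect, because withdrawals before radiation are already replaced. This also stands, apart from the gap in step 7.

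**Conclusion.** The concern holds as a bias in the DLT count. After radiation starts, the written rules keep under-exposed subjects in the cohort as non-DLTs, and escalation and the MTD use that count alone. With 30% stopping in the extreme case, P(pass) is 0.69 instead of 0.49 at a true in-field rate of 30%, and 0.95 instead of 0.91 at 10%. If stopping does not lower in-field risk, there is no change. The handling of subjects follows from the text; the sizes rest on assumed rates and independence.

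Two stronger readings are not supported. A reader might infer that an untolerated dose goes automatically into Phase 2; the RP2D rule in 3.1 allows a lower dose, although only by judgment. A reader might also measure the harm against a rule that counts every out-of-field exit against the dose. The protocol deliberately excludes those events from DLT, and the change below does not count them, so such a comparison would not describe its effect.

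**What to change.** - Leave the DLT definition unchanged.
- Define DLT-evaluable: the subject had a DLT, or completed the DLT window with a pre-stated minimum share (sponsor to set) of the assigned cabozantinib doses during radiation. Replace anyone else without a DLT, whatever the reason for stopping or reduction.
- Because replacement alone does not make the 3+3 respond to intolerance, tabulate lead-in exits, replacements and out-of-field Grade 3+ events by dose level. Require review of that table at each escalation decision and at the RP2D decision.
- Reconcile 3.1, 4.1 and 10.2.1 on who is in the DLT period, including withdrawals between C1D8 and a delayed radiation start.

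The cost is protocol wording and possibly a few more Phase 1 subjects: the limit of up to 12 would become up to 12 DLT-evaluable subjects.
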